## 1. Background

### ■ Importance of Microbiome Research

- ▷ The gut microbiome is a vast community of microorganisms residing in the digestive system, including bacteria, viruses, fungi, and other microbes that play a crucial role in maintaining overall health.
- ▷ Research on the microbiome is known to be associated with a wide range of health conditions, including obesity, diabetes, autoimmune diseases, and even mental health disorders such as depression and anxiety.
- ▷ It has also been shown to play a significant role in the onset of allergies and asthma. ▷ One of the key ways the gut microbiome influences health is by interacting with the immune system, helping to train it to recognize and respond to threats such as harmful bacteria and viruses. Therefore, disruptions in the balance of gut microbes can increase the risk of immune dysfunction, infections, and other health issues.
- ▷ Additionally, the microbiome is involved in the digestion and absorption of nutrients, breaking down complex carbohydrates and other compounds that cannot be digested by the body on its own to facilitate nutrient absorption.
- ▷ Therefore, research on the gut microbiome is essential for understanding the underlying mechanisms contributing to disease onset and identifying potential therapeutic approaches. Changes in diet and lifestyle can alter the composition of the gut microbiome, highlighting the potential for therapeutic interventions targeting this microbial community.

### ■ Importance of Research on Intractable Liver Diseases

- ▷ Chronic intractable liver diseases such as non-alcoholic fatty liver disease (NAFLD), non-alcoholic steatohepatitis (NASH), and cirrhosis are characterized by progressive liver damage, which can lead to the necessity of liver failure and transplantation. However, there are currently no approved therapies that can effectively halt or reverse the progression of liver damage in patients with progressive diseases, resulting in high unmet medical needs.
- ▷ To address these issues, it is crucial to better understand the underlying mechanisms that cause liver damage. Liver fat accumulation in NAFLD and NASH is believed to induce inflammation and oxidative stress, leading to the death of liver cells and their replacement with scar tissue. However, the exact molecular pathways mediating these processes are not fully understood.
- ▷ Additionally, there is a need to identify biomarkers that can accurately predict disease progression and response to treatment. Current methods such as liver biopsy, while necessary for diagnosing liver diseases and staging, are invasive and not suitable for monitoring disease progression over time.
- ▷ From a therapeutic perspective, there is an urgent need for therapies that can effectively halt or reverse liver damage in patients with progressive diseases. Current treatments for NAFLD and NASH, such as weight loss and

lifestyle modifications, are effective for some patients but often insufficient once the disease has progressed. Therefore, there is a critical need to target specific pathways associated with liver damage and develop therapies capable of halting or reversing disease progression.

- ▷ Primary sclerosing cholangitis (PSC) and primary biliary cholangitis (PBC) also represent chronic cholestatic liver diseases with significant unmet medical needs. Despite relatively low prevalence, they have high morbidity and mortality rates, and there are currently no approved therapies capable of effectively halting or reversing liver damage.
- ▷ In PSC, the immune system attacks the bile ducts, leading to inflammation and fibrosis, but the exact triggering factors are poorly understood, necessitating research into the molecular pathways involved. Similarly, in PBC, immune-mediated attacks on small bile ducts cause inflammation and fibrosis, and while autoimmune involvement appears critical, exact triggering factors remain unclear.
- ▷ Current treatments for PSC and PBC involve ursodeoxycholic acid and immunosuppressants; however, effective therapies that can effectively halt or reverse liver damage are needed. Moreover, given the variability in disease severity and treatment response, a more personalized approach to treatment is warranted.

#### ■ The Utility of Gut-Liver Axis Research for Chronic Intractable Liver Diseases

- ▷ The gut-liver axis refers to bidirectional communication between the liver and gastrointestinal tract mediated by various signaling molecules and cellular pathways. The gut microbiome can regulate liver function and metabolism through the production of diverse metabolites such as short-chain fatty acids and bile acids. Conversely, the liver generates bile secreted into the intestine to aid in fat digestion and absorption, and bile acids also act as signaling molecules that can modulate gut microbiota and intestinal immune function.
- ▷ Dysregulation of the gut-liver axis has been implicated in the onset of non-alcoholic fatty liver disease (NAFLD) and inflammatory bowel disease (IBD), and understanding the underlying mechanisms mediating this interaction could lead to the development of novel therapies targeting specific pathways associated with the gut-liver axis.
- ▷ Therefore, this study aims to identify specific gut microbiome profiles unique to patients with chronic intractable liver diseases and to conduct gut-liver axis research related to etiology and disease progression.

#### 2. Data collection method

We will collect a total of 20cc of venous blood and 5cc of stool (using a stool collection kit) from each consenting participant (patients and cohabitants living together) at three time points: at the time of the patient's disease diagnosis, 3-6 months after the patient's disease treatment, and 6-12 months after the patient's disease treatment.

### 3. Selection and Exclusion Criteria for Study Participants (Samples), Target Sample Size, and Justification

#### A. Selection Criteria

Adults aged 19 years and older diagnosed with autoimmune hepatitis, primary biliary cholangitis, primary sclerosing cholangitis, non-alcoholic fatty liver disease, or liver abscess, who have consented to participate in this study at Chungnam National University Hospital.

Adults aged 19 years and older, who are cohabitants of patients diagnosed with autoimmune hepatitis, primary biliary cholangitis, primary sclerosing cholangitis, non-alcoholic fatty liver disease, or liver abscess, and have consented to participate in this study at Chungnam National University Hospital.

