#### B. Exclusion Criteria

Individuals under the age of 19.

Patients or guardians who do not consent to participate in the study

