### B. Consent Process for Research Participants

- ▷ Research participants will be explained and consent will be obtained before collecting human specimens for the study.
- Person providing consent: Research participants
- Waiting time between explanation and consent process: 1-2 hours
- Language used by the researcher during the explanation and consent process: Korean
- Research participants will be provided with a research information sheet and consent form.
- ▷ We will conduct the study on those who have signed the consent form for this study among those who visited Chungnam National University Hospital, and explain that there will be no coercion or compulsion to participate and that there will be no undue influence on treatment even if they do not participate.
- ▷ For research subjects aged 65 and older (patients and patients' cohabitants), we will explain the purpose, background, and methods of the study in simple terms and with sufficient time to obtain their consent. In addition, we will obtain

consent from guardians or representatives after explaining the purpose, background, and methods of the study sufficiently to them.

- ▷ If a patient's cohabitant who cannot visit the hospital refuses to participate in the study or if the patient lives alone, only the patient will be registered as a research subject.

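### Sample 1 is defined as taken at diagnosis, but eligibility admits patients diagnosed at any earlier time, who cannot give it

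*Protocol*

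**What the plan says.** - **Eligibility (Protocol, 3.A and 3.B).** Patients are "Adults aged 19 years and older diagnosed with autoimmune hepatitis, primary biliary cholangitis, primary sclerosing cholangitis, non-alcoholic fatty liver disease, or liver abscess"; consent at the study hospital is also required. A parallel criterion admits adult cohabitants of such patients. The exclusions are "Individuals under the age of 19" and "Patients or guardians who do not consent to participate in the study". Neither list mentions time since diagnosis or earlier treatment.
- **Sampling (Protocol, section 2).** Blood and stool are taken from patients and cohabitants "at the time of the patient's disease diagnosis, 3-6 months after the patient's disease treatment, and 6-12 months after the patient's disease treatment". Cohabitants are thus timed by the patient's clock.
- **Recruitment and consent (Protocol, 5.B).** "We will conduct the study on those who have signed the consent form for this study among those who visited Chungnam National University Hospital"; and "consent will be obtained before collecting human specimens for the study".
- **Aim (Protocol, section 1, gut-liver axis).** To find microbiome profiles specific to these patients and to "conduct gut-liver axis research related to etiology and disease progression".
- **Data and analysis (Protocol, section 4).** The list of observational items includes past medical history and present illness, but does not name date of diagnosis, disease duration or start of treatment. Section 4.3 uses unspecified clinical data to stratify or classify patients. Section 4.4 groups by primary diagnosis and looks for taxa that differ between diseases, without naming a time point.

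**The concern.** The schedule presupposes patients met at diagnosis, while the eligibility criteria describe anyone who already carries the diagnosis. A recruiter working from 3.A can enrol a patient diagnosed years ago, for whom the first scheduled sample no longer exists.

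Two things are at stake. The first is what the baseline means: if some first samples come from established or treated disease, neither an at-diagnosis comparison nor a change from diagnosis has a clear interpretation. The second is the comparison between diseases. The protocol's background describes several of the conditions as chronic. If the mix of new and long-standing cases differs by diagnosis, disease duration is confounded with diagnosis, and a larger sample does not remove that bias. The moment of collection cannot be recovered afterwards.

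**Working it through.** **Step 1. Trace one patient through the text.** Take an adult diagnosed several years ago who now attends the hospital and consents.

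| Protocol section | Result for this patient |
|---|---|
| 3.A Selection | Eligible: has the diagnosis, is an adult, has consented |
| 3.B Exclusion | Not excluded: neither criterion applies |
| 5.B Recruitment | Reachable: a consenting hospital visitor |
| 5.B Consent | No specimen may be taken for the study before today |
| 2 Sampling | Sample 1 was due years ago and cannot be taken |

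No section resolves this. Two outcomes fit the text: sample 1 is missing, or a present-day sample is filed as sample 1. The cohabitant's sample 1 is tied to the same past date.

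**Step 2. Reproduce the plan's own figure.** Section 3.C gives effect size 0.25, alpha 0.05, power 0.95 and 417 per group. A two-sided two-sample t-test with d = 0.25 solves at n = 416.8, so 417 is reproduced. With 500 recruited and the stated 20% loss, 500 × 0.8 = 400 per group remain, and power is 94%. The conflict does not alter the 417.

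**Step 3. Illustrate the effect of pooling.** The documents give neither the share p of previously diagnosed patients nor the fraction r of the effect that they retain. Both are assumptions: p = 25%, 50%, 75% and r = 1, 0.5, 0. The standard deviation and the controls are taken as unchanged.

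Pooled effect: d = 0.25 × [1 − p(1 − r)]. Power comes from the two-sided t-test with noncentrality d × √(n₁n₂/(n₁+n₂)).

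Example: p = 0.5, r = 0.5 gives d = 0.25 × 0.75 = 0.1875; at 400 v 400 the noncentrality is 0.1875 × √200 = 2.65 and power is 75%.

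| Analysis | p = 25% | p = 50% | p = 75% |
|---|---|---|---|
| Pooled, 400 v 400, r = 1 (d = 0.25) | 94% | 94% | 94% |
| Pooled, 400 v 400, r = 0.5 (d = 0.219, 0.188, 0.156) | 87% | 75% | 60% |
| Pooled, 400 v 400, r = 0 (d = 0.188, 0.125, 0.063) | 75% | 42% | 14% |
| New cases only (300, 200, 100) v 400 controls, d = 0.25 | 90% | 82% | 61% |
| New cases only v equal controls (300, 200, 100), d = 0.25 | 86% | 70% | 42% |

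**Step 4. Read the table.** The last row is the relevant one for restriction, because cohabitants of previously diagnosed patients have the same timing problem and would leave the comparison with them. Against that row, restriction gains power only if r is near 0. At r = 0.5 it loses a little (86, 70, 42% against 87, 75, 60%), and at r = 1 it loses more. The table covers patient against control. The possible bias between diseases cannot be quantified from the documents.

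**The case against.** The strongest reply is that section 2 asks every consenting participant for a sample at diagnosis and 5.B puts consent first, so together they imply enrolment at diagnosis. That may well be the intention. It does not settle the matter, because 3.A and 3.B are the criteria by which people are enrolled and they do not say so.

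A second reply is that past medical history and present illness could yield disease duration, that section 4.3 foresees stratification by clinical data, and that the choice of strata may sit in an SAP that is not shown. This softens the point. But duration is not named as an item to collect, and no analysis plan can create a sample that was never taken.

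A reader might infer more than the documents support:

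- *That established-disease samples will be labelled as diagnosis samples.* The text permits this, but equally permits a missing sample; filing a late sample as sample 1 would itself depart from section 2.
- *That a planned diagnosis-time analysis is corrupted.* Section 4.4 names no time point, and the aims are not tied to sample 1.
- *That power will collapse.* The low figures need both a large share of previously diagnosed patients and a complete loss of effect in them.
- *That liver abscess cases are nearly all new while the other groups are mixed.* This is plausible clinically, but the protocol gives no case mix.

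**Conclusion.** The conflict between sections 2 and 3.A is real and should be corrected in the protocol. It concerns eligibility and the timing of collection, which are protocol matters. Any eligible patient diagnosed before enrolment has no valid sample 1, nor does the linked cohabitant, and disease duration could differ between the diagnosis groups being compared.

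The size is unknown. Under the assumed shares, pooling costs anything from nothing to most of the power, depending on how much of the effect persists in established disease, and restriction to new cases often does no better. The conclusion therefore rests on knowing what each sample represents and on avoiding bias from disease duration. It does not rest on a gain in power, and the stated sample size of 417 per group is unaffected.

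**What to change.** Reconcile sections 2 and 3.A as follows:

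1. State a window around diagnosis within which a sample counts as sample 1.
2. Record the date of diagnosis, and at each sample whether treatment of the disease had started.
3. Flag each patient, together with the linked cohabitant, as newly or previously diagnosed.
4. Label a first sample outside the window as established disease.
5. Use only newly diagnosed patients and their cohabitants for any at-diagnosis comparison or change from diagnosis. Stratify by the flag, or adjust for it, in comparisons between diseases.

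The cost is some protocol wording, a few data fields and a flag. Nobody need be excluded and nobody's care changes. The drawback is fewer participants in the at-diagnosis comparison: under the assumed shares, 300 to 100 patients per disease group against the 417 planned. The sponsor should estimate the expected share of newly diagnosed patients, so that this comparison is not presented as having the stated power if it does not.

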#### B. Exclusion Criteria

Individuals under the age of 19.

Patients or guardians who do not consent to participate in the study

#### C. Sample Size and Justification

##### 1) Sample Size: Total of 3,000 cases

Autoimmune Liver Diseases (patients diagnosed with autoimmune hepatitis, primary biliary cholangitis, primary sclerosing cholangitis): Experimental group 500 cases, Cohabitants control group 500 cases.

Metabolic Liver Diseases (patients diagnosed with non-alcoholic fatty liver disease): Experimental group 500 cases, Cohabitants control group 500 cases

Infectious Liver Diseases (patients diagnosed with liver abscess): Experimental group 500 cases, Cohabitants control group 500 cases

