### \* Observational Items, Clinical Examination Items, and Observation Methods

- Basal characteristics (age, gender, chief complaints, weight, past medical history, present illness, family history, alcohol consumption, smoking history)
- Hematological and serological/immunological markers (complete blood count results, serum alkaline phosphatase, AST, ALT, gamma-GT, total bilirubin, glycated hemoglobin, fasting blood glucose, lipid profile, IgM, IgG, antinuclear antibodies, anti-smooth muscle antibodies, anti-mitochondrial antibodies, HBsAg, HBeAg, HBcAg, HBs-Ab, anti-HBe, anti-HCV status)
- Imaging findings (CT scan, MRI, abdominal ultrasound, endoscopic retrograde cholangiopancreatography (ERCP) if applicable)
- Histopathological findings (pathological findings of liver biopsy tissue if applicable)

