### 4) Statistical Analysis Methods

Statistical analysis for the results of microbial species and distribution will involve Taxonomic profiling using the Galaxy platform, followed by LDA analysis. Grouping by primary diagnosis and deriving LDA Effect Size or utilizing MaAsLin2 functionality to identify taxa showing significant compositional changes between diseases. For transcriptome and metabolome results, categorical variables will be analyzed using the Chi-square test, while continuous variables will undergo t-tests. Correlation analysis will employ Pearson's coefficient.

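### The NAFLD group's alcohol intake may differ from its comparators' by design, and the named transcript and metabolite tests cannot adjust for it, so alcohol-related features can be reported as NAFLD-specific

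*Protocol*

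**What the plan says.** Protocol section 3.C.1 sets up three disease groups, each with its own cohabitant controls. The metabolic group is "Metabolic Liver Diseases (patients diagnosed with non-alcoholic fatty liver disease): Experimental group 500 cases, Cohabitants control group 500 cases". The other two are "Autoimmune Liver Diseases (patients diagnosed with autoimmune hepatitis, primary biliary cholangitis, primary sclerosing cholangitis): Experimental group 500 cases, Cohabitants control group 500 cases" and "Infectious Liver Diseases (patients diagnosed with liver abscess): Experimental group 500 cases, Cohabitants control group 500 cases".

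Eligibility (section 3.A) rests on a listed diagnosis, or on living with such a patient, plus adult age and consent. The cohabitant criterion begins "Adults aged 19 years and older, who are cohabitants of patients diagnosed with autoimmune hepatitis" and adds no condition on drinking. Section 3.B has two exclusions: "Individuals under the age of 19" and "Patients or guardians who do not consent to participate in the study". Neither concerns alcohol.

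The list of observational items in section 4 includes "family history, alcohol consumption, smoking history" among the baseline characteristics.

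For taxa, section 4.4 (Statistical Analysis Methods) plans "Grouping by primary diagnosis and deriving LDA Effect Size or utilizing MaAsLin2 functionality to identify taxa showing significant compositional changes between diseases". The same section names the Chi-square test for categorical transcript and metabolite variables and the t-test for continuous ones. It mentions no covariate for any of these analyses. Section 4.3 says in general terms that clinical data will serve to stratify or classify patient groups. It names no variable and does not mention cohabitants.

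**The concern.** A non-alcoholic diagnosis implies an upper bound on drinking. If the bound applies to one group only, group membership and alcohol intake can be linked by the selection rule itself. This affects NAFLD against the other diseases and NAFLD against its own cohabitants. Such a link differs from chance imbalance because it does not fade as the sample grows.

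Alcohol plausibly affects gut bacteria, plasma metabolites and blood gene expression. A feature that responds to alcohol but not to fatty liver could therefore separate NAFLD from a comparator and be read as part of the NAFLD profile. The study's purpose, in section 1 and section 4.3, is to find profiles specific to each disease, so an error of this kind bears directly on its main product. The variable needed to guard against it is already on the list of items to be recorded.

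**Working it through.** **1. The plan's own figure.** Section 3.C.2 gives an effect size of 0.25, alpha 0.05 and power 0.95, leading to 417 per group. A two-sided two-sample t-test with these inputs needs 416.8, so 417. The figure reproduces. It also shows the scale of difference the study is meant to detect: 0.25 SD.

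**2. Which groups have an alcohol limit.**

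| Group | Limit on alcohol in the protocol |
|---|---|
| NAFLD patients | None stated; implied by the name of the diagnosis |
| Autoimmune patients | None |
| Liver abscess patients | None |
| All cohabitants | None |

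**3. Which stated analyses can use alcohol.**

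| Data | Named method | Room for alcohol |
|---|---|---|
| Transcripts, metabolites | t-test, Chi-square test | None; these tests take no covariate |
| Taxa | LDA Effect Size, or MaAsLin2 | MaAsLin2 can take covariates; none is named |

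**4. Illustrative size.** The documents give no drinking distribution for any group and no effect of alcohol on any feature. Assumptions, none from the documents:

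- share of comparators above a NAFLD-type limit, p = 10%, 20% or 30%; share of NAFLD patients above it, 0%;
- shift in a feature among those above the limit, e = 0.2, 0.5 or 1.0 SD;
- no true NAFLD effect on the feature;
- m = 400 evaluable per group, which is 500 × (1 − 0.20). The 20% loss is the protocol's allowance for stool; I carry it over to blood for illustration.

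Formulas:

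- spurious difference = p × e
- pooled SD = √(1 + e²·p(1 − p)/2), which adds the spread from mixing drinkers and non-drinkers in the comparator
- SE = pooled SD × √(2/m)
- rejection probability = Φ(z − 1.96) + Φ(−z − 1.96), with z = p·e/SE

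Worked case, p = 0.30 and e = 0.5: difference 0.15; pooled SD = √(1 + 0.25 × 0.21/2) = 1.013; SE = 1.013 × √(2/400) = 0.0716; z = 2.09; probability 0.55.

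| e (SD) | p | Spurious difference (SD) | Significant at 0.05, 400 per group | Same, 500 per group |
|---|---|---|---|---|
| 0.2 | 10% | 0.02 | 6% | 6% |
| 0.2 | 30% | 0.06 | 14% | 16% |
| 0.5 | 10% | 0.05 | 11% | 12% |
| 0.5 | 20% | 0.10 | 29% | 35% |
| 0.5 | 30% | 0.15 | 55% | 65% |
| 1.0 | 20% | 0.20 | 78% | 86% |
| 1.0 | 30% | 0.30 | 98% | over 99% |

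The nominal rate is 5%. These are rates per alcohol-sensitive feature at an uncorrected 0.05. A stricter threshold lowers them: at an illustrative 0.001 per feature, the 29% and 55% entries fall to about 3% and 12%. At the top of the range the spurious difference (0.30 SD) exceeds the 0.25 the study is sized for; at the bottom (0.02 SD) it is negligible. Moving from 400 to 500 per group raises the rates, because the bias stays fixed while the standard error falls.

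**The case against.** **Covariates belong in the SAP.** Covariate lists are commonly left to an analysis plan, and one may exist here. For taxa this largely stands: section 4.3 allows stratification by clinical data and MaAsLin2 accepts covariates, so adjustment is permitted and only unspecified. It does not stand for transcripts and metabolites. There the protocol has already fixed tests that cannot adjust, and a SAP that added alcohol would depart from it.

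**A limit in one group is not a difference between groups.** This is right. A reader might infer that alcohol differences will appear as NAFLD findings, and against every comparator. The documents do not support that. They give no definition of NAFLD, no intake threshold and no drinking data. The limit is inferred from the disease name, and the absence of a limit elsewhere does not show that the other groups drink more.

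**The magnitude is all assumption.** This also stands. At a 0.2 SD effect the rate is 6-14% at 400 per group, not far from nominal, and any multiplicity correction lowers all the figures.

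**Alcohol is one confounder among several.** Age, sex, weight and smoking are recorded and unnamed in the analysis too. What sets alcohol apart is its link to the selection rule, which is reason enough to name it.

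**The remedy may not be free.** The item list gives no unit for alcohol and does not say that cohabitants are asked. Some entries, such as chief complaint and present illness, suit patients only. It cannot be assumed that usable intake data will exist for all groups.

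**Conclusion.** The concern holds in a limited form. One group is selected on a diagnosis that implies restricted drinking, no other group is restricted, alcohol is a recorded item, and no stated analysis uses it. Followed as written, the plan can attribute alcohol-related features to NAFLD. The point is firmest for transcripts and metabolites, where the named tests rule out adjustment. For taxa it is a matter of making a permitted adjustment explicit.

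The size cannot be established from the documents. Under the assumed 10-30% share and 0.2-1.0 SD effect, the per-feature false-positive rate at an uncorrected 0.05 and 400 per group runs from about 6% to about 98%. That range shows the problem can be anything from trivial to serious; it does not predict what will happen. The sample size calculation is not in question on this point. The change should be made because the better method is simple and rests on an item already listed.

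**What to change.** In section 4.4, for every contrast that involves the NAFLD group:

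- replace the t-tests with linear models, and the Chi-square tests with logistic regression, each including recorded alcohol consumption;
- base claims about NAFLD taxa on MaAsLin2 with alcohol as a covariate, and treat LDA Effect Size results as descriptive;
- repeat the contrasts, as a sensitivity analysis, among participants of all groups below one common intake. The cut-off must be stated in advance, since the protocol contains no NAFLD limit to borrow.

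In the list of observational items, state that alcohol consumption is recorded as an amount, and for cohabitants as well as patients.

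Cost: one more questionnaire item for cohabitants if it is not already asked, and fewer comparators in the sensitivity analysis. No additional participants are needed. If intake is poorly measured or its form in the model is wrong, some confounding will remain, so a return to the nominal 5% is the best case.
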